# 8.7 REPORTING OF SERIOUS ADVERSE EVENTS BY INVESTIGATOR TO IEC/IRB

The timeframe within an IEC/IRB must be notified of a death or an unexpected SAE considered at least possibly related to the IMP is stipulated by each individual IEC/IRB. The investigator is

Confidential Page 77 of 175

responsible for complying with the requirements for IEC/IRB notification. The investigator will notify the relevant IEC/IRB within the applicable timeframe by forwarding the safety report (eg, MedWatch/CIOMS form) completed by the sponsor for the notifiable event.

# 8.8 REPORTING OF EVENTS OTHER THAN SERIOUS ADVERSE EVENTS BY INVESTIGATOR TO SPONSOR

Even if none of the criteria for an SAE are fulfilled, any of the following events must be reported by the investigator to the Medical Monitor within 72 hours from the time the investigator is notified.

- 1. Hypersensitivity reactions
- 2. Pulmonary hypertension
- 3. Cardiac symptoms requiring intervention, or valvulopathy, if identified outside of study-related monitoring

# 8.9 FOLLOW-UP OF ADVERSE EVENTS

Every effort should be made to follow-up subjects who continue to experience an AE or an SAE on completion of the study or until the AE resolves. All follow-up information (and attempted follow-up contacts) should be documented in the subject's medical records. Details of the subject's progress should also be submitted to the sponsor's Global Clinical Safety and Pharmacovigilance and the Medical Monitor. In the event of a SAE a blood sample for ZX008 and AED PK should be collected as soon as feasible.

Subjects who are discontinued from the study or complete the study and have been found to have any signs of valvulopathy or pulmonary hypertension on ECHO will be followed until the condition has resolved or stabilized where no further changes are likely, for a minimum of

6 months from the last dose of study medication, unless it is determined after unblinding that the subject did not receive ZX008.

#### 8.9.1 Follow-up of Echocardiogram Findings

All ECHOs will be evaluated by a central reader from BioMedical Systems, Inc. (BMS), in consultation with the IPCAB, if warranted. Findings related to pulmonary hypertension or valvulopathy on any of the four valves (aortic, mitral, pulmonary, triscuspid) will be reported to the investigator with grades of normal, trace, mild, moderate or severe. If the ECHO result has progressed in severity since the last reading then new oversight measures will be enacted as described below in Levels 1-3. Table 12 describes the severity of ECHO findings with the level of increasing oversight if the subject is to remain in the study.

Table 12: Clinical Measures Enacted Upon Increasing Severity of ECHO Findings

	Valve			
Severity	Aortic	Mitral	Pulmonary	Tricuspid

Confidential Page 78 of 175

Normal	Level 1	Level 1	Level 1	Level 1
Trace	Level 2	Level 2	Level 1	Level 1
Mild	Level 2	Level 2	Level 1	Level 1
Moderate	Level 3	Level 3	Level 3	Level 3
Severe	Level 3	Level 3	Level 3	Level 3

# Level 1: Continue per protocol

#### Level 2:

- 1. If there is a desire to continue study medication:
  - a. The investigator will evaluate the efficacy to date based on study diaries and consult with the parent/guardian, and determine whether study treatment was associated with significant, meaningful benefit in number, severity and/or duration of seizures and/or on the impact on daily functioning.
  - b. The investigator will consider whether the subject has had reasonable trials (dose and duration) of other available anticonvulsants (e.g., valproic acid, clobazam, or topiramate), alone or in combination, and not maintained the level of seizure control achieved with study medication.
- 2. If the investigator feels consideration of continued treatment is warranted considering benefit and potential risks, and the parent/guardian feels strongly that the child be maintained on the study medication when understanding the risks, the parent/guardian must sign a new consent which describes the additional risks and the child should provide assent if appropriate.
  - a. If both of these conditions are not met, the subject is discontinued from treatment
- 3. The investigator prepares a case history and rationale for continuation to be submitted to the IDSMC for review, including consideration of effects on seizures and comorbidities.
- 4. The Co-Chairs of the IPCAB are alerted to the request and prepare, after consultation with BMS, an evaluation of the cardiopulmonary risks and proposed monitoring plan if applicable, for submission to the IDSMC.
- 5. IDMSC will review the submissions from the Investigator and the IPCAB and unblind the subject treatment if warranted.
- 6. IDSMC makes a determination of appropriate path, including the possible outcomes:
  - a. Discontinue study medication
  - b. Increase frequency of ECHO and ECG monitoring
  - c. Add additional ECG and/or ECHO measures to be monitored
  - d. Reduce the dose of study medication

#### Level 3:

1. The investigator will evaluate efficacy to date based on study diaries and consult with the parent/guardian, and determine whether the achieved benefit justifies the consideration of continuing study treatment by the IDSMC. MINIMAL efficacy criteria for IDSMC

Confidential Page 79 of 175

#### consideration:

- a. Seizures must be more than 75% improved (number of convulsive seizures per 28 days) on treatment over baseline, and improvement must be consistent.
- b. The number, type, duration, and distribution of seizures at baseline should be of a severity, which justifies the risks of cardiopulmonary complications, considering the subject's age and overall health.
- c. Subject has had reasonable trials (dose and duration) of other available anticonvulsants (eg, valproic acid, clobazam, topiramate), alone or in combination, and not maintained the level of seizure control achieved with study medication.
- 2. If the investigator feels consideration of continued treatment is warranted considering benefit and potential risks, and the parent/guardian feels strongly that the child be maintained on the study medication when understanding the risks, the parent/guardian must sign a new consent which describes the additional risks and the child should provide assent if possible.
  - a. If both of these conditions are not met, the subject is discontinued from treatment.
- 3. The investigator prepares a case history and rationale for continuation to be submitted to the IDSMC for review, which includes effects of study medication on seizures and comorbidities related to Dravet syndrome.
- 4. The Co-Chairs of the IPCAB are alerted to the request, and in consultation with BMS prepare an evaluation of the risks and proposed monitoring plan if applicable for submission to the IDSMC.
- 5. IDSMC will review the submission from the Investigator and the IPCAB and unblind the subject treatment if warranted.
- 6. IDSMC makes a determination of appropriate path, including these possible outcomes:
  - a. Discontinue study medication
  - b. Increase frequency of ECHO and ECG monitoring
  - c. Add additional ECG and/or ECHO measures to be monitored
  - d. Reduce the dose of study medication

#### 8.10 PREGNANCY

This study is open to female and male subjects. Whenever possible, a pregnancy in a female subjects or the female partner of a male subject exposed to IMP should be followed to term so as to assess any potential occurrence of congenital anomalies or birth defects. Any follow-up information, including premature termination and the status of the mother and child after delivery, should be reported by the investigator to the sponsor using a pregnancy reporting/outcome form.

### 9. DATA HANDLING PROCEDURES

#### 9.1 RECORDING OF DATA

The investigator (or delegate) will maintain individual records for each subject. These records

Confidential Page 80 of 175

should include dates when a subject visited the study site, study-required information and data, and other notes as appropriate. These records constitute source data.

An eCRF and a subject diary will be provided by the sponsor (or delegate) for each subject enrolled into the study. Study site staff will enter data directly into the validated electronic data capture (EDC) system by completing the eCRF via a secure internet connection. The investigator is responsible for ensuring accurate and proper completion of the eCRF and subject diary for recording data according to the instructions given in the eCRF and subject diary.

All entries in the eCRF must be backed up by the relevant source data at the study site. All source data will be kept according to all applicable regulatory requirements (see Section 12.8). Source data must be completed legibly for each subject enrolled into the study and signed by the investigator (or delegate).

Data entry in the eCRF and subject diary must be completed in a timely manner so that they always reflect the latest observations on the subjects enrolled in the study.

The subject's diary will be completed by the parent/caregiver at home. Data entries will be reviewed by the investigator for completion and consistency.

# 9.2 DATA QUALITY ASSURANCE

An initiation meeting will be held before starting the study, during which the study design, procedures to be followed, and measures for ensuring standardized performance will be explained by a delegate from the sponsor, and a common understanding of the requirements of the study will be reached with the investigator and other relevant personnel at the study site.

Data generated throughout the study will be monitored and the data entered in the eCRFs will be checked against the subject records for completeness and accuracy. The sponsor's study monitor will perform this function.

The computer system used for study data handling will be fully FDA 21 CFR Part 11 compliant. All creation, modification or deletion of electronic study records will be documented through an automated Audit Trail. Following completion of eCRF pages and entry of the data into a database, the data will be checked electronically for consistency and plausibility. Data queries will be generated for questionable data and response clarification will be sought from the investigator. These data queries must be resolved in a timely manner by the investigator (or delegate).

#### 9.3 RECORD RETENTION

A study document binder will be provided by the sponsor for the investigator at each site for all requisite study documents (constituting the "Investigator Study File").

Following completion of the study, the investigator will retain copies of the approved study protocol, ICF, relevant source documents, and all other supporting documentation related to the study according to applicable regulatory requirements.

The investigator is responsible for archiving the Investigator Study File, the subject's records, and

Confidential Page 81 of 175

the source data according to applicable regulatory requirements. These documents have to be archived for at least 15 years or at least 2 years after the last approval of a marketing application in an ICH region, but should be retained for longer if required by regulatory requirements or by agreement with the sponsor.

If the investigator can no longer maintain the archive of study records (eg, due to retirement or relocation), the sponsor must be informed in writing about any change in responsibility for record retention, including the name of the new responsible party, contact information, and location of the study records. Records may not be destroyed without prior written consent from the sponsor.

### 10. STATISTICS

#### 10.1 DETERMINATION OF SAMPLE SIZE

The results of the only randomized, placebo-controlled studies in subjects with Dravet syndrome can be found in the European Public Assessment Report (EPAR) for stiripentol (EMA, 2007). The EPAR summarizes the results from two studies: STICLO France and STICLO Italy. In the stiripentol groups, the SD of the percentage change in seizure frequency from baseline to month 2 was 42% in the French trial and 26% in the Italian trial. The analogous SDs for placebo groups were 38% and 62%. An SD of 50% was assumed for the primary analysis in this trial comparing ZX008 0.8 mg/kg/day to placebo on the change from baseline in seizure frequency. Using a two-sided test at the  $\alpha$ =0.05 significance level, a sample size of 35 subjects per treatment group affords 90% power to detect a difference in mean change from baseline of 40 percentage points. Similar assumptions and calculations yield a requirement for an additional 35 subjects in the 0.2 mg/kg/day ZX008 group. Thus, the total sample size is planned to be 105 subjects (35 per arm).

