# **Sample Size Determination:**

The results of the only randomized, placebo-controlled studies in subjects with Dravet syndrome can be found in the European Public Assessment Report (EPAR) for stiripentol (EMA, 2007). The EPAR summarizes the results from two studies: STICLO France and STICLO Italy. In the

Confidential Page 21 of 175

stiripentol groups, the standard deviation (SD) of the percentage change in seizure frequency from baseline to month 2 was 42% in the French trial and 26% in the Italian trial. The analogous SDs for placebo groups were 38% and 62%. An SD of 50% was assumed for the primary analysis in this trial comparing ZX008 0.8 mg/kg/day to placebo on the change from baseline in seizure frequency. Using a two-sided test at the  $\alpha$ =0.05 significance level, a sample size of 35 subjects per treatment group affords 90% power to detect a difference in mean change from baseline of 40 percentage points. Similar assumptions and calculations yield a requirement for an additional 35 subjects in the 0.2 mg/kg/day ZX008 group. Thus, the total sample size is planned to be 105 subjects (35 per arm).

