#### Efficacy

Primary Efficacy Analysis: The primary efficacy endpoint is the change in the mean convulsive seizure frequency (MCSF) per 28 days during the T+M periods compared with Baseline. The MCSF will be calculated from all available data collected during the Baseline and treatment periods. The primary endpoint will be analyzed using an analysis of covariance (ANCOVA) model with treatment group (three levels) and age group (< 6 years, ≥6 years) as factors, and with Baseline MCSF as a covariate. The primary analysis will compare the ZX008 0.8 mg/kg/day group to the placebo group using a two-sided test at the alpha=0.05 level of significance. The primary endpoint will also be analyzed using a nonparametric method and if normality assumptions are not met, the results of the nonparametric analysis will be used for evaluation of the primary endpoint. An additional analysis will be performed to assess the sensitivity of the primary analysis to changes in concomitant AED medications that may occur during the course of the trial. Specifically, the primary analysis will be repeated with a factor added to indicate whether a subject had a change in concomitant AED medication during the T+M period. Safety

All safety data will be appropriately analyzed by treatment group. The number and percentage of subjects with AEs will be displayed by body system and preferred term using the Medical Dictionary for Regulatory Activities (MedDRA). Summaries in terms of severity and relationship to study drug will also be provided. Adverse Events of Special Interest (AESI) and Serious AEs (SAEs) will be summarized separately in a similar manner. Laboratory tests, vital signs, physical

Confidential Page 22 of 175

examinations, neurological examinations, ECG, Doppler echocardiogram, C-SSRS, Tanner Staging results, etc, will be summarized appropriately, by treatment. All safety summaries will be based on the Safety Population.

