### 10.5.1 Efficacy Analyses

# 10.5.1.1 Primary Efficacy Analysis

The primary efficacy endpoint is the change in the mean convulsive seizure frequency (MCSF) per 28 days between the Baseline and T+M periods. The MCSF will be calculated from all available data collected during the Baseline or T+M Periods.

The primary endpoint will be analyzed using an analysis of covariance (ANCOVA) model with treatment group (three levels) and age group (< 6 years,  $\geq$ 6 years) as factors, and with baseline frequency as a covariate. The primary analysis will compare the ZX008 0.8 mg/kg/day group to the placebo group using a two-sided test at the  $\alpha$ =0.05 level of significance.

Since the ANCOVA used in the primary analysis relies on assumptions of normality, the primary endpoint will also be analyzed using a nonparametric method that does not require as stringent assumptions. A test such as the van Elteren test, which extends the Wilcoxon rank sum test to include stratified data, will be used to compare the ZX008 0.8 mg/kg/day group to the placebo group while stratifying for age group. If normality assumptions are not met, the results of the van Elteren test will be used to assess the primary objective.

An additional analysis will be performed to assess the sensitivity of the primary analysis to changes in dose or type of concomitant AED medications that may occur during the course of the trial, which are protocol violations. Specifically, the primary analysis will be repeated with a factor added to indicate whether a subject had a change in prescribed dose or type of concomitant AED medication during the T+M period. Further exploratory analyses may be conducted if changes in concomitant AED medication appear to have a significant impact on the primary outcome.

Additional analyses will compare the changes between the baseline MCSF and the MCSF measured independently during the Titration Period alone and the Maintenance Period alone.

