### 10.5.1.2 Key Secondary Analyses

The first key secondary endpoint – the proportion of subjects who achieve a  $\geq$ 40% reduction from baseline in convulsive seizure frequency – is derived directly from the primary endpoint. That is, the proportion of subjects in the ZX008 0.8 mg/kg/day group who have a change in convulsive frequency of at least -40 percentage points will be compared to the analogous proportion in the placebo group. The comparison will be made using a logistic regression model that incorporates the same factors and covariates as the ANCOVA used in the primary analysis. The second secondary endpoint – the proportion achieving a  $\geq$ 50% reduction in convulsive seizures – will be analyzed similarly. The analyses will be performed using data collected over the T+M period.

The longest interval between convulsive seizures will be calculated for each subject over the entire T+M period. The ZX008 0.8 mg/kg/day and placebo groups will be compared using a log-rank test.

Confidential Page 84 of 175

The MCSF in the ZX008 0.2 mg/kg/day group will be compared to the placebo group using the same methods employed for the primary analysis. Analyses of other key secondary endpoints involving the ZX008 0.2 mg/kg/day group will employ similar methods as those used to compare ZX008 0.8 mg/kg/day to placebo. Whenever feasible, secondary analyses involving either ZX008 0.8 mg/kg/day or ZX008 0.2 mg/kg/day will be repeated using post-treatment data collected during the Titration Period alone and during the Maintenance Period alone.

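### The 90% power is calculated for percentage change in seizure frequency, but the primary endpoint as written is the change in seizures per 28 days, so the stated power is not the power of the primary test

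*Protocol*

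**What the plan says.** Three parts of the protocol bear on this.

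- **Sample size (section 10.1, repeated in the synopsis under Sample Size Determination).** The SDs come from two stiripentol trials. For the stiripentol arms, "the SD of the percentage change in seizure frequency from baseline to month 2 was 42% in the French trial and 26% in the Italian" one. The placebo arms had 38% and 62%. The plan then assumes 50% for its own primary comparison. Both places conclude that 35 per arm "affords 90% power to detect a difference in mean change from baseline of 40 percentage points".
- **Primary endpoint (section 10.5.1.1, and the synopsis under Efficacy).** "The primary efficacy endpoint is the change in the mean convulsive seizure frequency (MCSF) per 28 days between the Baseline and T+M periods". It is analysed by ANCOVA with treatment, age group and baseline frequency, "using a two-sided test at the alpha=0.05 level of significance". Neither place mentions a percentage or a transformation. Both add that a nonparametric result decides if normality fails; section 10.5.1.1 names the van Elteren test.
- **Responder endpoint (section 10.5.1.2).** The 40% responder endpoint is said to come straight from the primary endpoint, and it counts subjects "who have a change in convulsive frequency of at least -40 percentage points".

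**The concern.** The sample-size section works in percentage points per subject. Read plainly, the primary endpoint is a difference in seizures per 28 days. The two are not interchangeable: the same percentage effect is a small count in a subject with few seizures and a large count in a subject with many.

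Randomization requires at least 6 convulsive seizures in the 6-week baseline (section 4.3), which is 6 × 28/42 = 4 per 28 days, and no maximum is set. Raw change is then driven by high-baseline subjects. Adding baseline as a linear covariate does not remove variance that grows with baseline.

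At stake is whether 35 per arm gives the primary comparison the power the protocol claims. Section 10.5.1.2 compounds the doubt, because its wording fits only a percentage endpoint.

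**Working it through.** **1. Reproduce the stated figure.** Inputs from section 10.1: n = 35 per arm, difference 40, SD 50, two-sided α = 0.05.

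- Normal approximation: 40 / (50 × √(2/35)) = 0.8 / 0.239 = 3.347. Power = Φ(3.347 − 1.960) = 0.917.
- Noncentral t with 68 degrees of freedom: 0.910.
- Needed for 90%: 2 × (1.960 + 1.282)² × (50/40)² = 32.8, so 33 per arm (34 by noncentral t).

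The arithmetic is correct, with difference and SD both in percentage units.

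**2. Carry the same effect to the endpoint as written.** At baseline b per 28 days, a 40-point difference is 0.4b seizures and an SD of 50% is 0.5b seizures.

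| Baseline per 28 days | 40-point difference (seizures) | SD of change (seizures) |
|---|---|---|
| 4 | 1.6 | 2 |
| 10 | 4 | 5 |
| 20 | 8 | 10 |
| 40 | 16 | 20 |

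At any single baseline the ratio is still 0.8, so the loss comes from the spread of baselines. Pooled over subjects, the effect is 0.4 × E(b) and the residual SD is roughly 0.5 × √E(b²). The standardized difference becomes about 0.8/√(1 + CV²), where CV is the coefficient of variation of baseline. With 35 per arm, 90% power needs about 0.775.

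- CV = 0.5 (assumed): 0.8/1.118 = 0.716; Φ(0.716/0.239 − 1.960) ≈ 0.85.
- CV = 1.0 (assumed): 0.8/1.414 = 0.566; Φ(0.566/0.239 − 1.960) ≈ 0.66.

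This is a rough guide to the ANCOVA only.

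**3. Simulate.** The protocol gives no baseline distribution, and no SD or target difference in seizures per 28 days, so all of the following is assumed: log-normal baseline truncated at 4 per 28 days; percentage change normal with mean 0 on placebo and −40 on 0.8 mg/kg/day, SD 50, floored at −100; 35 per arm.

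Power of ANCOVA on raw change (3,000 trials per setting):

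| Median baseline | log-SD 0.7 | log-SD 1.0 | log-SD 1.3 |
|---|---|---|---|
| 12 | 0.77 | 0.64 | 0.49 |
| 20 | 0.74 | 0.60 | 0.49 |

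Across repeated runs of these six settings the range was 0.46 to 0.80. ANCOVA on percentage change in the same data gave 0.90 to 0.92.

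**4. Apply the fallback rule.** The protocol names no normality check; Shapiro–Wilk on the ANCOVA residuals was assumed. Normality was rejected in 90% to 100% of trials, so the van Elteren result would nearly always decide. The full stated procedure had power of about 0.75 to 0.85.

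**5. A milder assumption.** With median 10 and log-SD 0.5, ANCOVA on raw change gave 0.83 and an unstratified rank-sum test 0.86. Both remain below 0.90.

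**The case against.** The strongest reply is that the protocol already guards against skewed raw change, because the nonparametric result decides when normality fails. This largely stands. A reader might infer from the ANCOVA figures that the trial has only about even odds of detecting a 40-point effect. The documents do not support that: where the ANCOVA does worst, it is the test the protocol would set aside. The fallback recovers much of the loss, though not all of it, and section 10.1 does not base its power on it.

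Second, the simulation generates data on the percentage scale with the same SD at every baseline. Percentage-change ANCOVA is then close to the generating model, and its 0.90 to 0.92 mostly returns the plan's own inputs. This stands too. A reader might infer that percentage change is shown to be the better primary variable; it is not. It is one of several defensible choices.

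Third, section 10.5 leaves the full methods to a SAP that is not at hand and could specify a transformation. That does not settle the point. The protocol itself fixes both the endpoint and the power claim, in different units, and no SAP can reconcile them without changing one.

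Finally, the percentage-point wording in section 10.5.1.2 could show that a percentage was always meant. In that case section 10.5.1.1 and the synopsis misstate the primary endpoint, and the contradiction remains.

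**Conclusion.** The mismatch of scale is certain. The 90% belongs to a comparison of percentage changes, not to the primary test as defined, and section 10.5.1.2 fits only the percentage reading.

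The size of the loss is not certain. Under the assumed baselines the full procedure has roughly 75% to 85% power, a miss rate of 15% to 25% against the stated 10%. The named ANCOVA alone has about 46% to 80%. These ranges depend on the assumed baseline distribution, the percentage-scale data model and the assumed normality check. They show that the stated power does not carry over; they do not estimate this trial's power. The sample-size arithmetic is correct on its own scale, and type I error does not depend on the units used in section 10.1.

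**What to change.** Before unblinding, put endpoint and power on one scale by one of two routes.

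1. Define the primary variable as percentage change in MCSF from Baseline to T+M in section 10.5.1.1 and the synopsis, keeping age group and baseline in the model. The calculation in section 10.1 then applies as it stands. A log-ratio is an alternative, but its SD and target difference would have to be stated on the log scale, with a rule for subjects with no seizures on treatment.
2. Keep change in seizures per 28 days, and replace the 90% in section 10.1 and the synopsis with the power for that endpoint. State its SD and target difference, and cover both the ANCOVA and the van Elteren fallback.

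Either way, align section 10.5.1.2 with the choice, including its statement that the responder endpoint derives from the primary endpoint.

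The cost is a change of wording and no added subjects. Under the first route the effect is reported as a percentage (or ratio), and raw change can stay as a descriptive summary. Under the second, the stated power may become less favourable.
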